Currently ongoing is the TRAAP 2 trial which started on March 3, 2018, and is expected to be completed in 2020. The targeted sample size is 4,524, in a multicentre double-blind randomized placebo-controlled trial. One gram of TXA or placebo is administered intravenously, slowly over 30 – 60 seconds, after administration of uterotonic, after the cord is clamped, within 3 minutes after birth. The investigators will assess the incidence of PPH (blood loss exceeding 1,000ml) following caesarean delivery (24).

In a local unpublished study conducted at Parirenyatwa and Sally Mugabe Central Hospitals, the pilot to this proposed study, the incidence of PPH was significantly lower in the TXA group compared to the control group in the per protocol analysis. The primary outcome occurred in 37(22.6%) of 164 women who received tranexamic acid and in 90 (31.4%) of the participants who did not receive tranexamic acid (p = 0.021).

There was no significant difference in the intention-to-treat analysis. The results showed a trend towards efficacy of tranexamic acid in preventing postpartum haemorrhage (25).

The available evidence suggests that routine TXA use before caesarean delivery may be a promising drug for the prevention of PPH, decreasing blood loss, and reducing the need for additional uterotonics and product transfusion with very mild adverse effects. However, the safest and most effective dosing, infusion rate, and timing of administration have yet to be determined (4).

JUSTIFICATION

TXA is already widely used in surgery to prevent clot breakdown to reduce blood loss (1). In the third stage of labour to prevent excessive bleeding, there are strong myometrial contractions that are potentiated by oxytocin; increased platelet action; as well as a massive release of coagulation factors with a concurrent increase in fibrinolysis. TXA can counter the fibrinolytic activity thereby facilitating coagulation (17). Its actions would therefore potentiate the effect of uterotonics already in use in reducing blood loss at caesarean section.

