PPH contributes to near-miss cases in addition to actual deaths, due to the serious complications that can occur as a consequence of serious PPH. These include adult respiratory distress syndrome, coagulopathy, shock, loss of fertility, and pituitary necrosis (Sheehan syndrome) (4). If PPH is prevented this could contribute towards reduced hospital stay, avoidance of expensive interventions for intractable PPH (such as hysterectomies and the need for blood products) and conserve our already strained resources.

Prophylactic TXA use has been shown to produce a statistically significant decrease in postpartum blood loss; however, this may not convey clinical significance in terms of transfusion rates and maternal comorbidity from severe haemorrhage. Currently, there is no consensus regarding the optimal timing or dosing of prophylactic TXA for caesarean deliveries (33).

In the light of the above, this research proposes to assess the efficacy of TXA in preventing PPH after caesarean delivery in a population large enough to be adequately powered to add to the current body of evidence. Also, there are no published RCTs, in Southern Africa reporting on TXA in obstetric patients.

GOAL STATEMENT

The aim of this study is to compare the effect of a low dose of TXA (1 g) at the time of skin incision during caesarean delivery together with prophylactic oxytocin administration, versus prophylactic oxytocin alone in an open label randomized clinical trial.

RESEARCH QUESTION

Does intravenous TXA 1g plus Oxytocin 10 IU result in a lower incidence of primary postpartum haemorrhage compared to Oxytocin 10 IU alone after caesarean section?

OBJECTIVES

- 1. To assess the effect of TXA (1g) on postpartum blood loss at caesarean delivery.
- 2. To determine the potential adverse effects of intravenous TXA administered at caesarean section.

PRIMARY OUTCOME

Incidence of PPH, defined by a calculated estimated blood loss > 1000ml or a red blood cell transfusion up to day 2 postpartum

Secondary Outcomes

- Other outcome measures describing postpartum blood loss including
 - o calculated blood loss,
 - visually estimated blood loss,
 - o mean/median number of units of packed red blood cells transfused,
 - o incidence of postpartum shock;
 - o proportion of women requiring supplementary uterotonics,
 - o incidence of postpartum transfusion,
 - o incidence of emergency surgery for PPH including caesarean hysterectomies,

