Study Setting

The study will be performed at two tertiary institutions that are affiliated to the University of Zimbabwe that serve as referral centres for clinics located in Harare as well as district and provincial hospitals in the surrounding provinces: Sally Mugabe Central Hospital Maternity Unit and Parirenyatwa Group of Hospitals i.e. Mbuya Nehanda Maternity Hospital (MNMH). Most of these patients understand both English and Shona languages.

Sample size

The sample size has been calculated assuming a proportion of 2.1% PPH in the experimental group and 5.8% (34) in the control group at 95% confidence interval and 90% power using the Fleiss formula giving a minimum sample size of

$$n = \frac{\left[\frac{Z_{\alpha}\sqrt{(r+1)\overline{p}\overline{q}} + Z_{\beta}\sqrt{rp_{1}q_{1} + p_{2}q_{2}}\right]^{2}}{r(p_{1} - p_{2})^{2}}$$

$$n = \frac{\left[\frac{1.96\sqrt{(1+1) \times 0.0395 \times 0.9605} + 1.28\sqrt{0.021 \times 0.979 + 0.058 \times 0.942}\right]^{2}}{(0.021 - 0.058)^{2}}$$

= 581 per group

Thus, total minimum sample size N = 1, 162 women

Where: n = sample size

 Z_{α} = 1.96 at 95% confidence interval

```
\alpha = probability of a type I error (significance level) = 0.05 \beta = probability of a type II error (1 – power of test)
```

 p_1 = proportion of PPH in the experimental group = 0.021

 p_2 = proportion of PPH in the control group = 0.058

r = ratio of control group/population 2 to experimental group/population 1

q = 1-p

Randomization

A randomized allocation to study and control groups using computer-generated random numbers will be prepared by the trial statistician.

Pharmacy Plan

Oxytocin iv is dispensed weekly from the pharmacy to theatre, where it is stored in a refrigerator in the custody of the sister in charge. All patients undergoing caesarean delivery routinely receive 10IU oxytocin iv, administered slowly by the anaesthetist after delivery of baby at Sally Mugabe Hospital Maternity Unit and Mbuya Nehanda Maternity Hospital. Cold chain will be maintained up to the administration of drug to the patient.

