Preoperative haematocrit will be determined on the day before elective caesarean or on the day of emergency caesarean delivery. Postoperative haematocrit will be the haematocrit obtained by blood sampling at D2 (on the second morning after caesarean section). If haematocrit is not available at D2, then haematocrit at D3 will be considered; if it is also missing, then the postpartum haematocrit closest to D2 in the absence of transfusion will be considered (36,37).

All women who receive RBC transfusion for PPH between delivery and D2 postpartum are defined to have PPH and meet the criteria for the primary outcome. Calculated blood loss is impossible to determine for these women. Moreover, women only rarely receive an RBC transfusion for a blood loss less than 1000 ml. As a marker of significant maternal morbidity, RBC transfusion is considered equivalent or superior to blood loss greater than 1000 mL(25).

Although visual estimation is the method used frequently by anaesthetists to estimate blood loss, it has been demonstrated as inaccurate in repeated studies. The estimate of blood loss is affected by amniotic fluid as well. Its continued use in clinical practice is likely related to tradition and it being easily used. We will also take note of the visual estimate made by the anaesthetist, and by the operating surgeon, as this is the method used locally(6,38)(39)

Secondary outcome measures

Describing postpartum blood loss

1. Clinical

- a. Visually estimated blood loss
- b. proportion of women requiring supplementary uterotonic treatment
- c. incidence of postpartum transfusion
- d. mean number of RBC units transfused
- e. incidence of emergency surgery for PPH including caesarean hysterectomies
- f. incidence of hypovolemic shock related to PPH as determined by assessing BP and pulse
- g. incidence of transfer to ICU
- h. incidence of maternal death from any cause
- i. length of hospital stay.

2. Laboratory

- a. incidence of calculated blood loss > 500 mL and > 1500 mL
- b. mean total calculated blood loss
- c. mean peripartum change in haemoglobin (difference between haemoglobin before delivery and at D2)
- d. Haemoglobin drop > 2 g/dL (between haemoglobin before delivery and at D2) (34).

Describing adverse events

1. Clinical

a. Hemodynamic parameters (heart rate, blood pressure) 15, 30, 45, 60, and 120 min after delivery

- b. the occurrence of potential mild adverse effects of TXA in the operating room:
 - i. nausea
 - ii. vomiting

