 - iii. sensation of rings or spots of light in visual field
 - iv. dizziness
- c. the occurrence of potential severe adverse effects of TXA during the hospital stay and up to discharge
 - i. deep vein thrombosis, if the diagnosis is confirmed by Doppler ultrasound
 - ii. pulmonary embolism, if the diagnosis is confirmed by radiological examination
 - iii. myocardial infarction
 - iv. seizure
 - v. renal failure requiring dialysis
- d. any other unexpected adverse events

Data Management

The researcher and assistants will allocate each patient codes. No identifiers will be used. Any data collected will be stored in an office accessible only to the researcher and research assistants, as well as on a password-protected laptop computer.

data cleaning and entry

Completed questionnaires will be checked for validity, accuracy and completeness by the principal investigator before data entry into the computer.

Statistical methods and data reporting

Data analysis and reporting will be guided by the Consolidated Standards of Reporting Trials (CONSORT) and will be done by the researchers with the assistance of the statistician. (34).

The women's demographic characteristics and standard risk factors for PPH will be compared between the two groups.

The main analysis of the primary and secondary outcomes will be performed in the modified intention-to-treat (ITT) population, defined as women who undergo randomization and have a caesarean delivery (except if they withdraw consent or are deemed ineligible after randomization).

We will also analyse two separate per-protocol populations: women from the modified ITT population receiving a uterotonic and TXA (as specified in the protocol) (per-protocol group 1); the other will include women from the modified ITT population receiving a uterotonic and then tranexamic acid or no TXA in the 10min after delivery (per-protocol group 2; for a situation more consistent with routine clinical practice). The baseline characteristics of the trial participants, the management of the third stage of labour, and protocol adherence will be compared by descriptive statistics.

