Prior to the COVID 19 pandemic HMH delivered 1,335 pregnancies while a total of 535 pregnancies per month were delivered at MNMH. On average 60 elective and 250 emergency caesarean sections were done at HMH per month, while 80 elective and 210 caesarean deliveries on average are done at MNMH. Based on a review of the theatre delivery records during the period from April 2020 to August 2020 an average of 154 emergency caesarean sections were done monthly at MNMH, while an average of 149 emergency caesa were done at HMH. During this COVID period an average of 303 caesarean sections are being done per month. About 90% of these meet the inclusion criteria. Assuming a participation rate of 50% of these, an inclusion period of 8 months should make it possible to recruit 1,162 participants. Given that the lockdown conditions are being eased, with staff returning after industrial action, and that the hospitals are slowly reintroducing antenatal clinics, there should be an increase in caesarean sections (elective and emergency) across both institutions which may allow us to reach the targeted number in a shorter time period.

Impact of COVID-19

Coronavirus disease 2019 (COVID-19) has led to the deadliest pandemic observed in over 100 years (40). Healthcare workers and potentially researchers in obstetric wards are at a particularly increased risk for occupational exposure due to long periods of interaction with patients during labour, patient care involving multiple team members, the unpredictable occurrence of sudden obstetrical emergencies with their potential for unanticipated intubations in women undergoing labour and delivery. Presence on an obstetrical ward presents a real risk for infection to the research team (41).

At the point of recruitment, the researcher and team will employ a combination of standard contact and droplet precautions, with further precautions undertaken during aerosol-generating procedures such as recruitment of patients in labour (42).

The standard precautions are used to prevent or minimize transmission at all times. These include hand hygiene, appropriate use of personal protective equipment (PPE), safe handling of sharps, respiratory hygiene, occupational health and injection safety (42).

Transmission-based precautions – droplet or contact include:

hand hygiene which is the most essential aspect

- PPE which consists of gloves, gown, and a medical mask
- Safe waste management (42).

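### Does recruiting exactly the calculated minimum of 1,162 women leave the main analysis short of its stated 90% power?

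*Combined protocol and SAP*

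**What the plan says.** All references are to the combined protocol and SAP.

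- **Sample size.** Assumed PPH rates are 5.8% (control) and 2.1% (TXA), with z = 1.96, 90% power and equal groups. The result is 581 per group: "Thus, total minimum sample size N = 1, 162 women".
- **Feasibility.** The target is the same number: "an inclusion period of 8 months should make it possible to recruit 1,162 participants".
- **Statistical methods and data reporting.** "The main analysis of the primary and secondary outcomes will be performed in the modified intention-to-treat (ITT) population". That population is randomised women who have a caesarean, "except if they withdraw consent or are deemed ineligible after randomization". Women allocated TXA who do not receive it stay in; per-protocol populations are analysed separately.
- **Primary outcome measure.** A missing day-2 haematocrit is replaced by the day-3 value, and "if it is also missing, then the postpartum haematocrit closest to D2 in the absence of transfusion will be considered". Women transfused for PPH by day 2 count as events without a haematocrit.
- **Literature review (pilot at the same two hospitals).** "The primary outcome occurred in 37(22.6%) of 164 women who received tranexamic acid and in 90 (31.4%) of the participants" who did not receive it. This was the per-protocol comparison, reported as significant. For the other analysis: "There was no significant difference in the intention-to-treat analysis".
- **Justification.** The trial is to test TXA "in a population large enough to be adequately powered to add to the current body of evidence".

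**The concern.** A number described as a minimum and also used as the target leaves no margin. The plan itself provides for removing some randomised women, and its haematocrit rule gives no outcome to a woman with no postoperative sample and no transfusion. So fewer than 1,162 women will probably be analysed.

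Non-receipt of TXA could cost more than loss does, because the main analysis keeps those women and the observed effect shrinks towards zero. The pilot's pattern, significant per protocol but not by intention to treat, is what such dilution would produce. If it recurred, a non-significant main result could be read as evidence against TXA at 90% power when the real power was lower. For a trial justified by adequate power, that would matter.

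**Working it through.** **1. Reproduce the plan's figure.** Inputs from the Sample size section: p1 = 0.021, p2 = 0.058, difference 0.037, mean rate 0.0395.

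n = [1.96·√(2 × 0.0395 × 0.9605) + z_β·√(0.021 × 0.979 + 0.058 × 0.942)]² / 0.037²

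- The first term is 0.5399. The second is 0.3514 with z_β = 1.2816.
- n = (0.8913)² / 0.001369 = 580.3, so 581 per arm and 1,162 in total, as stated. With z_β rounded to 1.28, n = 579.8.

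**2. Power with 581 per arm.** By the same formula, power = Φ[(0.037 − 1.96·SE0)/SE1], with SE0 = 0.01143 and SE1 = 0.01138. This gives 90.0%. Exact enumeration of the uncorrected chi-square test gives 91.4%. The plan names chi-square or Fisher's test as appropriate. About 23 events per arm are expected (581 × 0.0395), which suits chi-square; Fisher's test would give 89.1% even with no loss.

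**3. Loss of analysed women.** The documents give no loss rate, so 5% and 10% are assumed. The last column uses the pilot's per-protocol rates (31.4% v 22.6%) in the formula.

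| Not analysed | n per arm | Formula | Exact chi-square | Pilot rates |
|---|---|---|---|---|
| 0% | 581 | 90.0% | 91.4% | 92.3% |
| 5% | 552 | 88.5% | 90.0% | 91.0% |
| 10% | 523 | 86.8% | 88.3% | 89.5% |

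**4. Non-receipt of TXA.** Assume a share c of the TXA arm is untreated and has the control rate, and that 2.1% describes full receipt. The TXA-arm rate is then (1 − c) × 2.1% + c × 5.8%.

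| c | TXA-arm rate | Formula, 581 per arm | Exact chi-square |
|---|---|---|---|
| 5% | 2.285% | 86.1% | 87.5% |
| 10% | 2.47% | 81.4% | 82.7% |

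With 10% non-receipt and 5% loss together, power is 79% (formula) or 81% (exact).

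**5. Does the pilot supply c?** The number who did not receive TXA is about 90/0.314 = 287, against 164 who did. If women were allocated 1:1 and grouped by treatment received, 225.5 were allocated to each arm and c = 1 − 164/225.5 = 27%. If they were allocated 1:2, the group sizes imply no non-receipt. The pilot's allocation ratio is not given, so it does not fix c. Nor does its non-significant intention-to-treat result cap the true effect. With 225.5 per arm and a control rate of 31.4%, a difference just short of significance (8.2 points) has a 95% interval from about 0 to 16.4 points.

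**6. What more women would cost.** The Feasibility figures give 303 × 0.9 × 0.5 = 136 women a month.

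- 5% loss: 581/0.95 gives 612 per arm, 1,224 in total, 62 more, about 0.5 month.
- 10% loss: 581/0.90 gives 646 per arm, 1,292 in total, 130 more, about 1 month.
- 10% non-receipt plus 5% loss: 790 per arm, 1,580 in total, 418 more, about 3.1 months.

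At 136 a month, 1,162 women already take 8.5 months.

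**The case for a change.** The strongest case for a change is that the plan foresees both loss and non-receipt and budgets for neither. A small inflation would cost about half a month to a month. The investigators should also hold the pilot's intention-to-treat data, from which a receipt rate could be taken. Non-receipt lowers power at the pilot's rates as well (86% at 10%, by the formula), so the point does not hinge on which pair of rates is true.

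Much of this stands. No allowance is stated, and many statisticians would have added one. Three things limit it:

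- **Loss alone costs little.** Outcomes are taken in hospital around day 2, the haematocrit rule has fallbacks, and transfused women are classified without a sample. At 5% loss the exact power is still 90.0%.
- **The larger shortfall depends on an unknown rate.** The plan reduces the risk of non-receipt by keeping study TXA in theatre to secure supply (Pharmacy Plan). The Sample size section does not say whether 2.1% is a fully treated or an as-allocated rate. If it is as-allocated, dilution is already in it and step 4 counts it twice.
- **The pilot sentence is weak evidence.** Its allocation ratio is missing, the reference list describes it as a study of elective caesareans, and its per-protocol p value recomputes as 0.046 rather than the printed 0.021.

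A mid-trial reset of the sample size would also be debatable in an open-label trial analysed by its own researchers.

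**Conclusion.** No change to the plan follows. The 90% is correct for what it describes: 581 women analysed per arm, with the assumed rates holding in the groups as analysed. Losses of 5% to 10% would take power to between 87% and 90%, depending on the basis of calculation, which would not alter how the trial is read. A fall to about 81% to 83% needs 10% non-receipt that 2.1% does not already reflect; the documents neither establish nor exclude this.

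The remedies on offer are to enrol more women or to add explanation. Enrolling more is a fair trade-off against a recruitment schedule with no spare capacity at current caesarean numbers; it does not correct an error. Misreading of a null result is limited because the plan reports relative risks and absolute risk differences with 95% confidence intervals, which show what the analysed sample can exclude. Analysts following CONSORT, as the plan intends, would report the numbers analysed and would read the 90% as a planning figure.

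This rests on loss staying near the assumed range and non-receipt being small. A known high non-receipt rate at these hospitals would reopen the question.

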 - o mean peripartum change in haemoglobin and haematocrit as well as haemoglobin drop > 2 g/dL,
 - o transfer to intensive care unit (ICU),
 - o or death from any cause.
- To assess potential adverse effects of TXA:
 - o Hemodynamic parameters,
 - o adverse gastrointestinal events, renal, hepatic, and coagulation function,
 - o and any venous or arterial thrombosis at any time during the woman's postoperative course.

METHODOLOGY

Research design

Open-label parallel randomized control trial.

Target population

Women undergoing caesarean sections at Sally Mugabe and Parirenyatwa Hospitals based on set inclusion and exclusion criteria.

Inclusion criteria

- Estimated gestational age of 37 weeks or more
- Live intrauterine foetus
- Elective or emergency caesarean delivery
- Signed informed consent

Exclusion criteria including any of the following factors or conditions identified prior to surgery

- History of coagulopathies or conditions predisposing them to thromboembolic phenomena,
- seizure history,
- autoimmune disease,
- placental abruption,
- placenta praevia,
- abnormally adherent placentae if identified on prenatal ultrasound,
- eclampsia or HELLP syndrome,
- known hypersensitivity to TXA,
- planned general anaesthesia,
- caesarean delivery for the second twin or second/third triplet(s) after vaginal birth of the first twin,
- poor understanding of English/Shona languages,
- those who have received anticoagulants in the week before delivery
- persons-under-investigation for COVID-19 and confirmed COVID-19 positive women.

Women will receive individual information in late pregnancy about the trial from obstetricians and midwives during antenatal clinic visits or from anaesthetists during the pre-caesarean visit, or both. Women may be pre-included (receive information and sign consent forms) for caesareans both before and during labour when the investigator considers that the woman is likely to have a caesarean delivery. The aim of pre-inclusion is to facilitate recruitment, particularly the recruitment of caesareans during labour, which may be decided upon and performed in emergency situations. Women recruited prior to emergency caesarean delivery (in labour) sign consent to have the caesarean section while in labour. We therefore consider that having received information about the trial during the antenatal period and on the labour ward, they will also be able to provide informed consent for inclusion into the trial at the same time.

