TXA obtained for the study will be kept in theatre. This is to ensure an uninterrupted supply of the drug for the study. The TXA vials will be kept in theatre in a locked drug cupboard accessible to the researcher and research assistants at the authorization of the sister in charge. A dispensing register for the drugs will be kept together with the drugs. Patient details and study number, amount of TXA dispensed and wasted will be entered into the study register for accountability and to guard against abuse.

Intervention

The participants in the intervention arm will receive generally from the anaesthetist or nurse anaesthetist TXA (1g), administered slowly (over 30 – 60seconds) at the time of skin incision. Participants in both the intervention arm and control group will receive the routine prophylactic 10 IU oxytocin intravenously at birth of the baby. All other aspects of management of the caesarean section will be identical in both arms (34).

Other aspects of the caesarean delivery

- The surgical team will decide on the administration of additional uterotonics and the management of PPH, in a manner consistent with local guidelines. In particular, the use of TXA for the treatment of PPH will be allowed and left to the practitioner's discretion according to the hospital protocol.
- Because the surgeon's level of experience may affect estimated blood loss during or after a caesarean delivery, the obstetrician's experience, categorized as senior resident medical officer, senior house officer, junior registrar, senior registrar or consultant will be recorded (34).

Assessment

Data will be collected and recorded on the data collection tool. Any adverse event will to be reported on the IRB adverse event reporting form.

Primary outcome measure

Estimated blood loss (EBL) will be determined using haematocrit, haemoglobin, and visual estimates.

Calculated estimated blood loss = estimated blood volume \times (preoperative haematocrit – postoperative haematocrit) / preoperative haematocrit. Where estimated blood volume (mL) = weight (kg) \times 85).

The calculation is an objective measure to estimate blood loss because of the inaccuracy of other methods used to determine blood loss and caesarean delivery(35).

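### Adverse effects are compared by randomised arm while treatment TXA is open to both arms; no supportive safety summary by TXA actually received is planned, and recording of non-study TXA is not specified

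*Combined protocol and SAP*

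**What the plan says.** - **Randomised exposure.** Under Intervention, the TXA arm receives "TXA (1g), administered slowly (over 30 – 60seconds) at the time of skin incision". Both arms receive routine oxytocin. The design is "Open-label parallel randomized control trial".
- **Treatment TXA.** Under Other aspects of the caesarean delivery, "the use of TXA for the treatment of PPH will be allowed and left to the practitioner's discretion according to the hospital protocol". Nothing limits this to one arm.
- **Safety outcomes.** The second objective concerns the adverse effects of intravenous TXA given at caesarean section. Adverse effects are listed under Secondary Outcomes. Mild effects are counted in the operating room, haemodynamic measures to 120 minutes after delivery, and severe effects (thrombosis, infarction, seizure, dialysis) until discharge.
- **Analysis.** Statistical methods and data reporting states: "The main analysis of the primary and secondary outcomes will be performed in the modified intention-to-treat (ITT) population". Two further populations are named: "women from the modified ITT population receiving a uterotonic and TXA (as specified in the protocol) (per-protocol group 1") and a second "receiving a uterotonic and then tranexamic acid or no TXA in the 10min after delivery (per-protocol group 2"). Third-stage management and protocol adherence are to be described. No safety or as-treated population is defined.
- **Recording.** For TXA obtained for the study, "Patient details and study number, amount of TXA dispensed and wasted will be entered into the study register". Supplementary uterotonic use is a secondary outcome; treatment TXA is not.

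**The concern.** A control woman who bleeds, is given TXA as treatment and then has a seizure or thrombosis is counted as a control-arm event, and no planned table shows her exposure. A woman in the TXA arm who has both a prophylactic and a treatment dose looks the same as one who had the prophylactic dose only. TXA given to controls makes the arms more alike in exposure, and for harm that error runs in the unsafe direction: a real adverse effect looks smaller. The second objective asks about TXA as administered, and the by-arm contrast answers a somewhat different question. Exposure not recorded at the time may not be recoverable later.

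**Working it through.** **Inputs.** From Sample size: 581 women per group, PPH 2.1% (TXA) and 5.8% (control). From the literature review, the pilot: "37(22.6%) of 164 women who received tranexamic acid and in 90 (31.4%) of the participants who did not receive tranexamic acid". Two inputs are not in the documents and are assumptions: *s*, the share of PPH cases given treatment TXA, taken as 25% to 100%; and *u*, the share of the TXA arm that misses the prophylactic dose, taken as 0% to 27.3%.

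The upper end of *u* comes from the pilot. 90/0.314 = 287 women did not receive TXA, so 164 + 287 = 451. If allocation was 1:1, each arm had 225.5 women, and 164/225.5 = 72.7% were dosed. This assumes that these 451 are all the women randomised and that the whole imbalance is non-receipt.

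**Plan's own figure.** The Fleiss formula with 2.1%, 5.8%, two-sided 0.05 and 90% power gives 581 per group with an unrounded z for power, and 579.8 with the printed 1.28. The stated size reproduces.

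**Dilution.** Suppose harm depends on any TXA exposure, with the same effect from either kind of dose.

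- Control exposure: c = s × control PPH rate.
- TXA-arm exposure: e = 1 − u + u·c (undosed women are treated at the control rate).
- Share of the true risk difference kept: e − c = (1 − u)(1 − c).

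| PPH rates | s | c | Exposed controls of 581 | Lost, u = 0 | Lost, u = 27.3% |
|---|---|---|---|---|---|
| Planning | 25% | 1.45% | 8 | 1.45% | 28.4% |
| Planning | 100% | 5.8% | 34 | 5.8% | 31.5% |
| Pilot | 25% | 7.85% | 46 | 7.85% | 33.0% |
| Pilot | 100% | 31.4% | 182 | 31.4% | 50.1% |

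In the last column, 27.3 points are missed prophylaxis. Treatment TXA adds only 0.727 × 5.8% = 4.2 points at planning rates with s = 100%, and 0.727 × 31.4% = 22.8 points at pilot rates.

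**Power, for illustration.** Assumed adverse-effect risks, 581 per arm:

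| Unexposed vs exposed | No dilution | Planning, s = 100%, u = 0 | Pilot, s = 100%, u = 0 | Pilot, s = 100%, u = 27.3% |
|---|---|---|---|---|
| 5% vs 10% | 90% | 86% | 56% | 35% |
| 1% vs 3% | 68% | 62% | 34% | 22% |

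**Two doses in the TXA arm.** With u = 0 the number is 581 × TXA-arm PPH rate × s: 3 to 12 women at planning rates, 33 to 131 at pilot rates. If harm adds per dose, the share kept at pilot rates with s = 100% is 1 + 0.226 − 0.314 = 91%, against 69% under the any-exposure model.

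**Per-protocol populations.** Group 1, as written, contains only women who received TXA, so it has no comparator. Group 2 looks at the 10 minutes after delivery. The scheduled dose is at skin incision, before delivery, so the window misses it, may catch an early treatment dose, and ignores later treatment. Neither is designated for safety.

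**The case against.** The strongest reply is that the by-arm comparison is the right main analysis. The stated goal is to compare adding TXA at incision with oxytocin alone, and leaving rescue treatment to usual care answers what the policy does. An as-treated contrast is confounded, because treatment TXA goes to women who bleed. This stands, and the modified ITT comparison should remain the main one.

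Other parts of the reply also stand:

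- **Tracking.** A reader might infer that TXA outside study stock is not tracked at all. The documents do not support that. The per-protocol populations and the adherence description need TXA receipt for each woman, and the data collection tool is not in the text. What can be said is that time, amount and reason for non-study TXA are not specified.
- **Double dosing.** A reader might infer that a second dose in the TXA arm dilutes harm. It does not; if risk rises with dose it widens the arm difference. The problem there is attribution.
- **Proxy.** PPH here is mostly a calculated loss from a day-2 haematocrit, while clinicians treat bleeding they recognise. The PPH rate is therefore only a rough guide to treatment TXA use.
- **Severe events.** The cited meta-analysis had 4 thromboembolic events in 2,345 caesareans; 1,162 × 4/2,345 is about 2. By-arm inference on so few says little, diluted or not. That favours a listing by exposure.
- **Mild effects.** These are counted only in the operating room, so only treatment given there can affect them.

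The per-protocol sentence can be read as covering adverse effects, adverse events go individually on the ethics board's form, and the DSMB reviews safety. None of these provides for treatment TXA to be shown by arm or for events to be set against exposure before onset.

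**Conclusion.** The point holds as a gap in recording and supportive reporting, and closing it is a cheap improvement. It is not an error in the main analysis. With full adherence, treatment TXA alone hides about 1-6% of a true difference at planning PPH rates, which is small, and 8-31% at pilot rates, which is material at the upper end. These ranges rest on the assumed 25-100% treatment share and on harm depending on any exposure.

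A reader might infer that treatment TXA shrinks a harm signal by 31-50%. The documents do not support that. Those values need 27.3% missed prophylaxis, which is ordinary non-adherence and not a result of allowing treatment TXA. They also need a 1:1 pilot whose imbalance was all non-receipt, and treatment of every PPH case. About 50% is the extreme of the range.

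**What to change.** 1. Keep the modified ITT comparison as the main safety analysis.
2. Record on the data collection tool every TXA dose from any stock up to discharge: time, amount, and whether for prophylaxis or treatment.
3. Report treatment TXA by arm, beside supplementary uterotonics.
4. Prespecify a supportive safety table and a listing of severe events by TXA exposure before onset: none, prophylactic only, treatment only, both. The four groups matter: a split by prophylactic dose alone would still place a control woman given treatment TXA among the unexposed. Give both to the DSMB.
5. Reconcile the window that defines per-protocol group 2 with the dosing time under Intervention, and state the comparator for group 1.

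The cost is a few data fields, one line in the by-arm results, one table and one listing. No treatment rule changes. The downside is that exposure groups are not protected by randomisation and treatment TXA is confounded by bleeding. The table should be labelled descriptive and should supplement the by-arm analysis.
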